#### **9.4.3 Interim Analyses**

No interim analysis is planned.

#### **9.4.4 Analysis Population**

**Per Protocol Population:** The study population for analysis will include all non-censored subjects who receive the study devices and are available for efficacy evaluation. For details regarding study devices, see Section 6.1 and 6.2.

The primary and secondary efficacy analyses will be based on the per protocol population.

**Safety Population:** The safety population will include all non-censored subjects who received the study devices. For details regarding study devices, see section 6.1 and 6.2. For details regarding protocol-defined AEs, see Section 8.1.

The safety analysis will be based on the safety population.

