**Termination Reason**

**Date of Termination**

Death	Date of death
Investigative center termination	Date of study close-out visit
Lost to follow-up	Date Stryker termination approval given
Voluntary withdrawal	Date subject notified center of withdrawal
Revision/removal of study device	Date of revision/removal procedure
Study device not implanted	Date of surgery
Surgery not performed	Date Stryker termination approval given

At the time of study surgery it is required that the following components are implanted for each treatment group:

- Cohort 1 (cementless)
  - Triathlon Tritanium Tibial Baseplate
  - Triathlon Tritanium Patella
  - Triathlon CR or PS Beaded Femur with PA
  - Triathlon Tibial Insert
  
- Cohort 2 (cemented)
  - Triathlon Cemented Tibial Baseplate
  - Triathlon Cemented Patella
  - Triathlon CR or PS Cemented Femur
  - Triathlon Tibial Insert

Revision or removal of the Triathlon Tritanium Tibial Baseplate for aseptic loosening constitutes a failure for purposes of the primary endpoint. Revision or removal of the Triathlon Tritanium Tibial Baseplate for any reason requires study termination for the subject.

If revision of the Triathlon Tritanium Patella, Triathlon Beaded Femur or Triathlon Tibial Insert component is required during the study, the event does not constitute a failure or study termination for Cohort 1 (cementless). If revision of the Triathlon Cemented Patella, Triathlon Cemented Femur or Triathlon Tibial Insert component is required during the study, the event does not constitute a failure or study termination for Cohort 2 (cemented).

CONFIDENTIAL

This material is the property of Stryker Orthopaedics. Do not disclose or use except as authorized in writing by Stryker.

If the subject fails to return for his/her follow-up appointments, every effort should be made to contact the subject to assess his/her health status. If, after attempting to contact the subject through three documented phone calls and a certified letter, and the subject still does not respond, he/she will be considered lost to follow-up. A Study Termination eCRF will be completed **only after notifying Stryker of the subject's status** and **being given approval to terminate**.

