**Appendix F**

**Draft Specifications for Electronic Case Report Forms**

Patient ID: 74 -  -

Patient Initials (if there's no middle initial please use a "-")

Termination Date: -- DD-MMM-YYYY

Operative Side Left Right

Study Termination

1. Did subject complete study according to protocol (Please choose one):
  - a.  Yes
  - b.  No (if no, please select primary reason below)
  
2. Primary reason for termination (Please choose one):
  - a.  Screen failure
  - b.  Death
  - c.  Investigative site termination
  - d.  Lost to follow-up
    - i. 1st phone call date: -- DD-MMM-YYYY
    - ii. 2nd phone call date: -- DD-MMM-YYYY
    - iii. 3rd phone call date: -- DD-MMM-YYYY
    - iv. Certified letter date: -- DD-MMM-YYYY
    - v. Additional efforts: \_\_\_\_\_
  - e.  Revision/Removal of the tibial baseplate
  - f.  Subject withdrawal
  - g.  Surgery not performed
  - h.  Other (specify): \_\_\_\_\_
  
3. Was study device in place at last contact (Please choose one):
  - a.  Yes
  - b.  No

Comments:

Investigator signature: \_\_\_\_\_ Date: -- DD-MMM-YYYY

Patient ID: 74 - □□ - □□□□

Patient Initials (if there's no middle initial please use a "-" ) □□□

Event Onset Date: □□-□□□□-□□□□ DD-MMM-YYYY

Operative Side Left Right

Adverse Event

1. When did event occur (Please choose one):

- a.  Pre-op
- b.  Peri-op
- c.  Post-op

2. Adverse event (Please choose one):

- a.  Arthrofibrosis
- b.  Deep joint infection
- c.  Excessive knee pain
- d.  Femoral fracture
- e.  Loosening femoral component
- f.  Loosening patella component
- g.  Loosening tibial component
- h.  Myositis ossificans
- i.  Patella component dislocation
- j.  Patella fracture
- k.  Patella subluxation
- l.  Patella tendon rupture
- m.  Peroneal nerve palsy
- n.  Prosthesis fracture / femoral component
- o.  Prosthesis fracture / patella component
- p.  Prosthesis fracture / tibial component
- q.  Prosthesis fracture / tibial insert
- r.  Reflex Sympathetic Dystrophy (RSD)
- s.  Soft tissue trauma
- t.  Superficial wound infection
- u.  Supracondylar fracture
- v.  Tibial component subsidence
- w.  Tibial fracture
- x.  Wound hematoma
- y.  Wound related (specify): \_\_\_\_\_
- z.  Operative site other (specify): \_\_\_\_\_
- aa.  Bronchopulmonary (event description): \_\_\_\_\_
- bb.  Carcinoma (event description): \_\_\_\_\_
- cc.  Cardiovascular (event description): \_\_\_\_\_
- dd.  Dermatological (event description): \_\_\_\_\_

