- ee.  Gastrointestinal (event description): \_\_\_\_\_
- ff.  Genitourinary (event description): \_\_\_\_\_
- gg.  Neurosensory (event description): \_\_\_\_\_
- hh.  Pulmonary embolism
- ii.  Thrombophlebitis
- jj.  Trauma (event description): \_\_\_\_\_
- kk.  Systemic other (event description): \_\_\_\_\_

3. Describe the event circumstances: \_\_\_\_\_

4. Device related (for Yes & uncertain a PER must be filed and Stryker must be contacted within 24hrs)

- a.  Yes
- b.  No
- c.  Uncertain

5. Seriousness

- a.  Resulted in inpatient hospitalization
- b.  Resulted in prolonged existing hospitalization
- c.  Resulted in persistent or significant disability/incapacity
- d.  Resulted in permanent impairment of a body function or permanent damage to a body structure
- e.  Necessitated medical or surgical intervention to preclude permanent impairment of a body function or permanent damage to a body structure
- f.  Was a life threatening situation
- g.  Resulted in subject death
- h.  None

6. Date AE became serious. If serious date is same as the onset date, enter the onset date:

-- DD--

Treatments

1.  None

2. Revisions/Removals:

- a.  Femoral component -- DD-
- b.  Tibial baseplate (complete termination form) -- DD-
- c.  Tibial insert -- DD-
- d.  Patellar component -- DD-

3. Reoperations

- a. Details/Description -- DD-
- b. Details/Description -- DD-
- c. Details/Description -- DD-

4. Other treatment:

- a. Details/Description -- DD-
- b. Details/Description -- DD-
- c. Details/Description -- DD-

5. Resolution of event:

6. Reoperations

- a. Unresolved as of -- DD-
- b. Resolved as of -- DD-

Comments:

Investigator signature: \_\_\_\_\_ Date: -- DD--

Patient ID: 74 -  - Patient Initials (if there's no middle initial please use a "-") Visit Date: -- DD-MMM-YYYYOperative Side Left RightDemographics

Subject Completed Section:

1. Education Level (Please choose one):

- a.  Less than high school
- b.  High school diploma
- c.  Greater than high school
- d.  Decline to answer

2. Employment Status (Please choose one):

- a.  Working
- b.  Not working
- c.  Decline to answer

3. Annual household income (Please choose one):

- a.  > \$24,999
- b.  \$25,000-\$49,999
- c.  \$50,000-\$74,999
- d.  \$75,000-\$99,999
- e.  \$100,000-\$149,999
- f.  > \$150,000
- g.  Decline to answer

4. Ethnicity (Please choose one):

- a.  Hispanic or Latino origin
- b.  Not Hispanic or Latino origin
- c.  Decline to answer

5. Race (Please select all that apply):

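### Section 9.4.4 limits the efficacy set to undefined non-censored subjects and applies it to the all-cause Kaplan-Meier curves, which depend on censored follow-up

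*Combined protocol and SAP*

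**What the plan says.** Section 9.4.4 (Analysis Population) defines two sets. For the per protocol population: "The study population for analysis will include all non-censored subjects who receive the study devices and are available for efficacy evaluation". It then states: "The primary and secondary efficacy analyses will be based on the per protocol population". For safety: "The safety population will include all non-censored subjects who received the study devices". The word *non-censored* occurs only in these two definitions and is explained in neither.

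For Cohort 1, sections 9.1.2 and 9.1.4 place among the secondary efficacy analyses the all-cause Kaplan-Meier curves for the baseplate and the patella, and the all-cause revision/removal rate of each. No section gives these analyses a different set. Section 9.2.1 also makes revision/removal rates a safety parameter.

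Sections 2.1.3, 7.5.1 and 7.5.2 say that the Follow-up Questionnaire is collected so that the Kaplan-Meier curves can be calculated. No section gives a censoring rule or a censoring date.

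Section 10.3 lists reasons for study termination, with a date for each, but does not say which of them make a subject censored. It adds: "Revision or removal of the Triathlon Tritanium Tibial Baseplate for any reason requires study termination for the subject". It also says: "Revision or removal of the Triathlon Tritanium Tibial Baseplate for aseptic loosening constitutes a failure for purposes of the primary endpoint". Under the same section, revision of the patella, femur or insert alone is neither a failure nor a termination.

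**The concern.** A Kaplan-Meier estimate uses the time that each knee was known to be unrevised, including knees whose follow-up later stopped. Those are the censored knees. Section 9.4.4 admits only subjects who are not censored, and adds the condition that they be available for efficacy evaluation. Taken at face value, the rule removes the follow-up that the questionnaires are meant to supply.

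What is at stake is the estimate. The synopsis and section 2.1.2 compare the all-cause baseplate and patella results with published results for cemented components, and Cohort 1 is followed to 10 years, when losses accumulate. That comparison has no stated margin or test, so a biased curve would mislead readers without altering a pre-specified decision.

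**Working it through.** **The plan's own figures.** Section 9.4.2 gives 267 cases before loss and 315 after 15% loss. With a 99% reference rate, a 2% margin, 5% one-sided significance and 95% power, n = 0.99 × 0.01 × (1.645 + 1.645)² / 0.02² = 267.85, and 267 / 0.85 = 314.1, rounded up to 315. Both figures reproduce. The 15% is the only loss figure in the document and refers to the 2-year endpoint. Cohort 1 has 356 cases.

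**Readings of the word.**
- A: knees lost event-free are dropped and revised knees are kept.
- B: subjects terminated early are dropped.
- C: the strict survival sense, in which only knees with an event are non-censored.
- D: an administrative meaning, such as removal of protocol violators.

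**Reading A.** Assume constant hazards and loss independent of revision. Let p be the true revision rate at time τ and d the proportion that would be lost by τ.
- λτ = −ln(1 − p) and γτ = −ln(1 − d)
- P(complete, unrevised) = (1 − p)(1 − d)
- P(revised while followed) = λ/(λ + γ) × [1 − (1 − p)(1 − d)]
- Rate reported = P(revised) / [P(revised) + P(complete)]

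For p = 2% and d = 15%: λτ = 0.0202 and γτ = 0.1625. P(complete) = 0.98 × 0.85 = 0.8330. P(revised) = (0.0202/0.1827) × 0.1670 = 0.01846. The rate is 0.01846 / 0.85146 = 2.17%. Of 356 knees, about 6.6 are revised, 296.5 complete and 52.9 lost.

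For p = 5% and d = 15%: P(complete) = 0.8075 and P(revised) = (0.0513/0.2138) × 0.1925 = 0.04618. The rate is 0.04618 / 0.85368 = 5.41%.

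| Assumed true revision | Loss by then | Rate with lost knees dropped |
|---|---|---|
| 2% at 2 years | 15% | 2.17% |
| 5% at 10 years | 15% | 5.41% |
| 5% at 10 years | 30% | 5.96% |
| 5% at 10 years | 40% | 6.44% |
| 5% at 10 years | 50% | 7.08% |

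The true rates, and every loss figure other than 15%, are assumptions. A simulation of 356 knees (1,500 runs, true 2-year survival 97%, 15% loss) gave an average of 97.0% for Kaplan-Meier on all knees and 96.75% with lost knees dropped.

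**Reading B.** Section 10.3 terminates the subject at any baseplate revision, so dropping early terminations leaves no baseplate revisions: 0% by construction. Isolated patella revisions do not terminate, so the patella curve would lose only those that accompany a baseplate revision.

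**Reading C.** Only revised knees remain, so the curve falls to zero survival.

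**Reading D.** Lost knees stay in as censored, and the word does no damage.

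**The primary rate.** Under reading A with 1% failure and 15% loss, the same formula gives 1.085%, a shift of 0.085 points against a 2-point margin. With 15% of 356 lost, about 302 remain (356 × 0.85 = 302.6). For 4 failures in 302, the 90% lower bound is 96.995% by the exact (Clopper-Pearson) method, 97.011% by log-log, 97.083% by Wilson and 97.593% by Wald. Section 9.1.3 names no method.

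**The case against.** The best defence is reading D. The set is labelled per protocol, yet nothing else in section 9.4.4 removes protocol violators. Section 11.6 lists consent deviations and ineligible enrolled patients, and section 11.2 mentions withdrawn authorization. None of these is covered by the requirement to have received the devices, so the word could be doing that job. This stands: incompatibility with Kaplan-Meier follows under some readings and is not certain.

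A second defence is that any statistician would censor in the usual way, since the questionnaires are collected for that purpose. The intent is indeed visible. But doing so departs from the written set, and the plan supplies no censoring date to replace it. The nearest candidate is the termination date in section 10.3, which for loss to follow-up is the date of the sponsor's approval. That can fall after the implant's status was last known and so credit unobserved event-free time.

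A reader might infer from readings B and C that the study would report 0% or 100% baseplate revision. The documents do not support that. Section 10.3 counts aseptic-loosening baseplate revision as a primary failure, and sections 9.2.1 and 12.3 call for revision/removal rates in the safety analysis, whose set carries the same word. These readings show how loose the wording is; they are not likely results.

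**Conclusion.** The point holds with moderate confidence and should be fixed. An undefined restriction governs the all-cause curves and rates without exception. In its ordinary sense, or as an exclusion of lost or early-terminated subjects, it biases them, and the direction depends on the reading.

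The credible size is that of reading A. At the plan's 15% loss the overstatement is 0.17 points on an assumed 2% at 2 years and 0.4 points on an assumed 5% at 10 years. It reaches about 2.1 points only at an assumed 50% loss. All of this rests on constant hazards, independent loss and assumed revision rates.

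A reader might also infer that the primary non-inferiority decision could flip. The documents do not support that either. With 4 failures in 302, the exact bound falls just under 97% and the log-log, Wilson and Wald bounds lie above it on the same subjects, so the difference comes from the interval method and not from the analysis set. No change in the primary decision is claimed. The aseptic-loosening curve in section 9.4.1 is also left out of this finding, because it appears there as a data summary with no analysis set stated.

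**What to change.** 1. Delete *non-censored* from both definitions in section 9.4.4. If it was meant to remove particular protocol violators, name them.
2. State that the Kaplan-Meier analyses use all Cohort 1 knees implanted with the study components, without the availability condition, separately for baseplate and patella.
3. Define the event as revision or removal of that component, at its date. Censor every other knee at the last visit or questionnaire with known implant status, and not at the termination date in section 10.3.
4. Keep the planned primary rate, with aseptic-loosening baseplate revisions counted as failures as section 10.3 already says. The 24-month Kaplan-Meier estimate may be added as supportive.

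The cost is wording and programming. The adverse event form in Appendix F already dates baseplate and patella revisions separately. The termination form asks "Was study device in place at last contact" of the device as a whole and shows no last-contact date, so status and date must come from visits, questionnaires and adverse event records. Whether the Follow-up Questionnaire separates baseplate from patella status cannot be checked from the documents and should be confirmed before the censoring rule is programmed.

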## **10 Study Procedures**

### ***10.1 Subject Recruitment and Screening***

Patients are recruited at the study centers during preoperative visits through normal referral patterns. All patients recruited for this study must have the capacity to give informed consent. Advertising for the study at each center will be at the discretion of the investigator. All handouts, brochures, advertisements, etc. must be approved by the IRB/EC prior to the dissemination of any recruitment materials to potential subjects. Study advertisement content may be found in Appendix D

### ***10.2 Patient Informed Consent and Guidelines***

All patients for this study are provided an Informed Patient Consent Form describing this study and providing sufficient information for them to make an informed decision about their participation. The Informed Patient Consent Form must contain all elements required by the FDA under 21 CFR Part 50, in addition to any other elements required by state, local and institutional policies. For international sites, the applicable country regulations are required. See Appendix E for a copy of the Model Informed Patient Consent. This is submitted with the protocol for review and approval by the IRB/EC for the study. All patients must provide written consent after having had adequate time to consider their participation in the study. The formal

CONFIDENTIAL

This material is the property of Stryker Orthopaedics. Do not disclose or use except as authorized in writing by Stryker.

consent of a patient, using the IRB/EC approved Informed Patient Consent Form, must be obtained before that patient is submitted to any protocol related procedures that are not part of normal care. Written documentation of consent must be provided on the Informed Patient Consent Form's signature page in addition to a note in the patient medical records indicating the date that consent was obtained. The investigator-designated research professional obtaining the consent must also sign this Informed Patient Consent Form. The patient or his/her legal representative should receive a signed copy of the Informed Patient Consent Form, according to GCP guidelines.

The procedure for obtaining informed consent is outlined below:

- Use a current IRB/EC approved copy of the Informed Patient Consent Form.
- Review thoroughly with the patient before having them sign.
- After the patient has consented to the procedures, ensure he/she signs and dates the Informed Patient Consent Form.
- The person obtaining consent also signs and dates the signature page.
- Provide a copy of the Informed Patient Consent Form to the patient.
- If required, provide the hospital with a copy of the signed Informed Patient Consent Form.
- Maintain the signed original in the patient's study chart.

### ***10.3 Early Withdrawal of Subjects***

#### **When and How to Withdraw Subjects**

In the event that the subject is discontinued by the investigative center prior to the final study evaluation, the subject is notified by the center that he/she is no longer in the study and a Study Termination eCRF will be completed.

The following is a list of reasons for which subjects may be withdrawn and the date of termination that should be used on the Study Termination eCRF in each situation. This list is not all inclusive:

**Termination Reason**

**Date of Termination**

Death	Date of death
Investigative center termination	Date of study close-out visit
Lost to follow-up	Date Stryker termination approval given
Voluntary withdrawal	Date subject notified center of withdrawal
Revision/removal of study device	Date of revision/removal procedure
Study device not implanted	Date of surgery
Surgery not performed	Date Stryker termination approval given

At the time of study surgery it is required that the following components are implanted for each treatment group:

- Cohort 1 (cementless)
  - Triathlon Tritanium Tibial Baseplate
  - Triathlon Tritanium Patella
  - Triathlon CR or PS Beaded Femur with PA
  - Triathlon Tibial Insert
  
- Cohort 2 (cemented)
  - Triathlon Cemented Tibial Baseplate
  - Triathlon Cemented Patella
  - Triathlon CR or PS Cemented Femur
  - Triathlon Tibial Insert

Revision or removal of the Triathlon Tritanium Tibial Baseplate for aseptic loosening constitutes a failure for purposes of the primary endpoint. Revision or removal of the Triathlon Tritanium Tibial Baseplate for any reason requires study termination for the subject.

If revision of the Triathlon Tritanium Patella, Triathlon Beaded Femur or Triathlon Tibial Insert component is required during the study, the event does not constitute a failure or study termination for Cohort 1 (cementless). If revision of the Triathlon Cemented Patella, Triathlon Cemented Femur or Triathlon Tibial Insert component is required during the study, the event does not constitute a failure or study termination for Cohort 2 (cemented).

CONFIDENTIAL

This material is the property of Stryker Orthopaedics. Do not disclose or use except as authorized in writing by Stryker.

If the subject fails to return for his/her follow-up appointments, every effort should be made to contact the subject to assess his/her health status. If, after attempting to contact the subject through three documented phone calls and a certified letter, and the subject still does not respond, he/she will be considered lost to follow-up. A Study Termination eCRF will be completed **only after notifying Stryker of the subject's status** and **being given approval to terminate**.

In the event a subject does not have surgery, Stryker should be contacted to discuss if/when the surgery will be rescheduled. If the surgery is rescheduled more than 4 months from the date of preoperative data collection, the subject will need to be re-consented, all preoperative data will need to be re-collected and all original preoperative data will need to be removed from the database. If the surgery is not to be rescheduled or if the subject is no longer considered an appropriate study candidate, a Study Termination eCRF may be completed **only after notifying Stryker of the subject's status** and **being given approval to terminate**.

When a subject completes the study according to protocol, including the final study evaluation, a Study Termination eCRF will be completed.

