## **7.5 Annual Follow-up Visits**

### **7.5.1 Cohort 1 (cementless) Annual Follow-up Visits**

Cohort 1 (cementless) will be followed to 10 years postoperatively according to the following schedule. Clinical data will be collected via office visit by the investigator at the following annual postoperative intervals: 1-year, 2-year 5-year and 10-year. Tools for postoperative evaluation at each of these intervals will be the 2011 KSS, OKS, SF-12, AP, ML and Merchant radiographs. In the event that an in-person visit cannot be conducted and radiographs cannot be obtained, a Follow-up Questionnaire will be completed via mail, online completion (if available), or subject telephone interview with the subject by investigative site personnel.

The Follow-up Questionnaire, OKS and SF-12 will also be collected at the 3-year, 4-year, 6-year, 7-year, 8-year and 9-year intervals via mail, online completion (if available), or subject telephone interview with the subject by investigative site personnel. The questionnaire is used to obtain information on satisfaction, pain, complications and any study device revisions to enable calculation of the Kaplan-Meier Survival Curves.

All clinical data, radiographs, and patient outcomes data must be collected within  $\pm$  2 months of the 1-year and 2-year anniversary dates. For remaining annual time points, the window expands to  $\pm$  3 months of the 3-year anniversary date and  $\pm$  4 months of the 4-year through

CONFIDENTIAL

This material is the property of Stryker Orthopaedics. Do not disclose or use except as authorized in writing by Stryker.

10-year anniversary dates.

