### **9.1.3 Primary Efficacy Analysis**

The primary hypothesis to be tested will be that the success rate at 2 years postoperative with the Triathlon Tritanium Tibial Baseplate for Cohort 1 (cementless) is not worse than 99% with a non-inferiority margin of 2%.

That is, the following hypothesis will be tested:

$H_0: Pt \leq 99\% - 2\%$   $H_A: Pt > 99\% - 2\%$

Here, Pt is the success rate at 2 years postoperative with the Triathlon Tritanium Tibial Baseplate for Cohort 1 (cementless).

A 90% two-sided confidence interval will be computed for the success rate at 2 years. If the lower bound of the confidence interval is greater than 97%, then the non-inferiority hypothesis will be supported.

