#### **9.4.2 Sample Size Justification**

With a reference value of 99% for the success rate at 2 years, under the assumptions of 5% significance level (or 95% one-sided confidence interval), 95% power, 2% non-inferiority margin, the sample size is 267. After factoring a 15% lost to follow-up rate, the final sample size is 315 for the primary endpoint. An enrollment objective of 356 cases in Cohort 1 (cementless) was selected to power the primary objective of this study. In addition, 144 cases will be enrolled in Cohort 2 (cemented) to serve as a concurrent control for one of the secondary objectives.

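### Section 10.3 lets a non-responder be terminated with no provision for renewed contact, so 2-year baseplate status that later scheduled questionnaires could establish is lost

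*Combined protocol and SAP*

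**What the plan says.** Section 10.3 first asks sites to try hard to reach a subject who misses follow-up appointments. It then gives the only defined threshold: "three documented phone calls and a certified letter, and the subject still does not respond, he/she will be considered lost to follow-up". The termination form follows once the sponsor has been told and has approved. Where a center discontinues a subject early, "the subject is notified by the center that he/she is no longer in the study and a Study Termination eCRF will be completed". The draft Study Termination form in Appendix F has date fields for three calls and one certified letter, a line for additional efforts, and a question on whether the device was in place at last contact. No section describes an attempt at the next interval, contact after termination, or a way back into the study.

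Sections 7.5.1 and 7.5.2 provide a remote tool. The Follow-up Questionnaire can be completed by mail, online or telephone when an office visit cannot be held. It is also scheduled at years 3 and 4 in both cohorts and at years 6 to 9 in Cohort 1. Its purpose is stated: "The questionnaire is used to obtain information on satisfaction, pain, complications and any study device revisions to enable calculation of the Kaplan-Meier Survival Curves".

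On the analysis side, Section 9.4.4 restricts the efficacy analyses to subjects who can be evaluated. Section 9.3 limits imputation to the OKS and 2011 KSS scores. No sensitivity analysis for knees of unknown status is given. Section 9.4.2 allows for attrition: "After factoring a 15% lost to follow-up rate, the final sample size is 315 for the primary endpoint".

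**The concern.** The primary endpoint is revision or removal of the tibial baseplate for aseptic loosening by 2 years. Such an event is permanent and dated, so 2-year status does not have to be observed at 2 years. A reply at year 3 or later that the original baseplate is still in place proves 2-year success. Few endpoints allow a missing value to be recovered so directly, and the questionnaire that would do it is already in the schedule.

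Under Section 10.3 a subject unreachable at 6 months or 1 year can be terminated and then has no planned contact at years 2, 3, 5 or 10. The analysis drops that knee. Failures are expected to be very few, so the conclusion can depend on a handful of knees nobody asked about again. The same losses feed into the 5- and 10-year survival curves.

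**Working it through.** **Inputs**
- Design (Section 9.4.2): "5% significance level (or 95% one-sided confidence interval), 95% power, 2% non-inferiority margin, the sample size is 267".
- Assumed success (Section 9.4.2): "With a reference value of 99% for the success rate at 2 years". The null boundary is 99% − 2% = 97%.
- Enrollment (Section 9.4.2): "An enrollment objective of 356 cases in Cohort 1 (cementless) was selected to power the primary objective of this study".
- Interval (Section 9.1.3): "A 90% two-sided confidence interval will be computed for the success rate at 2 years". The result passes if the lower bound exceeds 97%. The method is not named.

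**1. Reproduce the plan's figures.** Normal approximation with the variance at 0.99:

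n = (1.645 + 1.645)² × 0.99 × 0.01 / 0.02² ≈ 267.8, which is 267 when truncated.

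267 / (1 − 0.15) = 314.1, rounded up to 315. Both stated figures reproduce.

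**2. Knees of unknown status.** Assume the planned 15% loss applies to 356: 356 × 0.15 = 53.4, about 53 unknown, leaving about 303 completers. At the planned 1% failure rate, 303 × 0.01 ≈ 3 failures are expected among completers.

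**3. Lower 90% two-sided bounds.** With x failures in n, p = (n − x)/n and z = 1.645:
- Wald: p − z√(p(1 − p)/n)
- Wilson: [p + z²/2n − z√(p(1 − p)/n + z²/4n²)] / (1 + z²/n)
- Exact (Clopper-Pearson): 5% quantile of Beta(n − x, x + 1)

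| Failures / n | Wald | Wilson | Exact |
|---|---|---|---|
| 3 / 303 | 98.07% | 97.55% | 97.46% |
| 5 / 356 | 97.57% | 97.14% | 97.07% |
| 6 / 356 | 97.19% | 96.77% | 96.70% |
| 7 / 356 | 96.82% | 96.41% | 96.34% |

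The highest failure count that passes at n = 303 is 5 (Wald) or 4 (Wilson, exact). At n = 356 it is 6 (Wald) or 5 (Wilson, exact).

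**4. Failures among the 53 that would reverse a pass, if all 356 were known.** This is the limit at 356, plus 1, minus the failures observed in completers:

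| Observed in 303 | Wald | Wilson or exact |
|---|---|---|
| 0 | 7 | 6 |
| 1 | 6 | 5 |
| 2 | 5 | 4 |
| 3 | 4 | 3 |
| 4 | 3 | 2 |
| 5 | 2 | already fails |

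With 3 observed, reversal takes 3 of 53 (5.7%) under Wilson or exact, or 4 of 53 (7.5%) under Wald.

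**5. How likely that is.** The failure rate among lost knees is unknown, so a range is assumed. For X ~ Binomial(53, rate):

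| Assumed rate | P(X ≥ 3) | P(X ≥ 4) |
|---|---|---|
| 1% | 1.6% | 0.2% |
| 3% | 21% | 7.5% |
| 5% | 50% | 27% |

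**6. What a later contact can settle.** A report that the original baseplate is in place settles 2-year success. A report of a revision does not settle failure by itself. Sections 9.1.1 and 10.3 count only the tibial baseplate, and only aseptic loosening; patella, femur and insert revisions are not primary failures. Component, cause and date are all needed.

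**The case against.** The strongest reply is that the rule is neither automatic nor final. Section 10.3 asks for full effort first, speaks of missed appointments in the plural, and makes termination depend on sponsor approval. Appendix F has room for additional efforts. A missed 2-year office visit already has a remote route under Section 7.5, and Appendix H offers reminder letters, optional by site. No passage forbids later contact. All of this stands. A reader might infer that one unanswered round ends participation by itself, or that re-contact is barred; the documents say neither. What remains is that these safeguards act before termination, Section 10.3 gives no criteria for approval, and nothing is planned afterwards.

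A reader might also infer that three failures among the lost knees would reverse the primary result. That is not a figure from the plan. It needs 15% loss from 356, 3 failures in 303, and an exact or Wilson interval. Wald, the approximation that reproduces 267, needs 4, and across all passing cases the range is 2 to 7. If lost knees fail at the planned 1%, three or more failures among 53 has a probability of only 1.6%.

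Two further inferences lack support. The documents do not say that patients revised elsewhere are the ones who stop replying. Nor are all 53 knees recoverable: 15% is the only attrition allowance in Section 9.4.2, while Section 10.3 lists death and voluntary withdrawal as separate reasons, and renewed contact recovers neither.

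Finally, it can be said that the direct answer to a completer-only analysis is a sensitivity analysis. One would be useful, but it bounds the uncertainty, whereas repeat contact reduces it.

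**Conclusion.** The point holds as a cheap improvement to the follow-up rule. Once a subject is terminated as lost, the protocol plans no further contact and no re-entry, and Sections 9.3 and 9.4.4 drop the knee, although questionnaires already in the schedule could establish its 2-year status.

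The size is illustrative. It assumes 15% loss from 356 (about 53 knees, an upper bound for non-responders) and 3 failures in 303 completers. Then 3 failures (exact or Wilson) or 4 (Wald) among the lost knees would turn a pass into a failure. The documents do not support saying that this is likely, or that the primary result is biased.

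**What to change.** In Section 10.3, record non-response as a missed visit. Repeat the contact attempt (telephone, mailed or online questionnaire, letter) at each later scheduled interval, to 10 years in Cohort 1 and 5 years in Cohort 2. Complete the lost-to-follow-up termination only at the end of the subject's schedule. Voluntary withdrawal still ends contact.

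In Section 9.1.1 or 9.3, state how later information is used. A report that the original baseplate is in place sets 2-year success. A reported revision sets 2-year status only once the component (tibial baseplate), the cause (aseptic loosening or other) and the date are documented. Extend the Appendix F form to hold more than one round of attempts. Naming the interval method in Section 9.1.3 and adding a tipping-point analysis for knees still unknown would complete the change.

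The cost is protocol wording, a few extra calls or mailings per non-responder per year, and subject records that stay open longer. For subjects enrolled late, a year-3 reply may come after the 2-year results are compiled. For them the early gain is the retry at years 1 and 2, and later replies serve the longer-term survival curves.
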